6.3 Randomization

Blocked randomization will be used to randomize patients to either arm 1 or arm 2. A master sequence of randomization numbers for each arm will be generated.

7.0 Treatment Plan/Methods

This is a randomized open-label phase II trial; 116 triple negative breast cancer patients will be randomized equally between 1) Ixabepilone or 2) Ixabepilone plus Cetuximab. The study population will include patients≥ 18 years of age diagnosed with invasive mammary carcinoma. Patients will be assigned to treatment arms using a stratified blocked randomization, with strata based on disease stage (T1N1-3M0 or T2-4 N0-3M0). All patients will receive a physical assessment, imaging, a blood draw, and a core needle biopsy (CNB) a biopsy prior to the start of treatment.

7.1 Treatment Arm 1

Patients will receive Ixabepilone 40mg/m² given over approximately 3-hours on day 1 Patients will receive a total of four cycles of this combination with each cycle given 21(+/- 3) days.

Subjects will be premedicated approximately 1 hour before the ixabepilone infusion with either 1) both an oral H1 blocker (diphenhydramine 50 mg or equivalent) and an oral H2 blocker (e.g., ranitidine 150 300 mg or cimetidine 300–800 mg or nizatidine 150-300 mg or famotidine 20–40 mg); or 2) with premedication per institutional standards. Premedication with steroids is indicated in subjects who developed a hypersensitivity reaction to ixabepilone in previous cycles. Patients with severe reaction should not be retreated (see dose modification chart below).

7.2 Treatment Arm 2

Patients will receive Ixabepilone 40mg/m^2 given over approximately 3-hours on day 1 followed by Cetuximab given on day 1 at 400 mg/m² as an initial loading dose (first infusion) administered as a 120-minute IV infusion (maximum infusion rate 5 mL/min) followed by 250 mg/m² infused over 60 minutes (maximum infusion rate 5 mL/min) as a subsequent weekly dose. Patients will receive a total of 4 cycles of this combination with each cycle being 21 (+/-3) days.

Subjects will be premedicated approximately 1 hour before the ixabepilone infusion with either 1)both an oral H1 blocker (diphenhydramine 50 mg or equivalent) and an oral H2 blocker (e.g., ranitidine 150-300 mg or cimetidine 300–800 mg or nizatidine 150 300 mg or famotidine 20–40 mg); or 2) with premedication per institutional standards. Premedication with steroids is indicated in subjects who developed a hypersensitivity reaction to ixabepilone in previous cycles. Patients with severe reaction should not be retreated. Subjects who are to receive cetuximab are to be premedicated with an H₁ antagonist (e.g., 50 mg of diphenhydramine IV or equivalent)

7.3 Dose modifications:

7.3.1 Ixabepilone dose modifications:

The dose of Ixabepilone may be decreased depending on how well the patient tolerates the study treatment. Subjects should be evaluated during treatment by periodic clinical observation and laboratory tests including complete blood cell counts. If toxicities are present, treatment should be delayed to allow recovery.

If toxicities recur, an additional 20% dose reduction should be made.

The dose levels of Ixabepilone will be reduced as described in the table below:

Dose Level	Ixabepilone	
1	(Starting Dose) 40 mg/m ²	
-1	32 mg/m ²	
-2	25 mg/m ²	

Patients requiring dose reductions below dose level -2 must discontinue Ixabepilone, with the following exception: Patients with responding disease may continue treatment on study after consultation with the sponsor, TMHRI. No dose re-escalation will be allowed after dose reduction.

Dose Modification - Study Drug Related Non-Hematologic Toxicities

Toxicity	Ixabepilone
Grade 2	
Grade 2 except Gr 2	No change
Neuropathy lasting ≥□7	
days ^a	
Grade 2	Decrease 1 dose level b,c
Neuropathy	
lasting ≥⊡7 days	

Dose Modification - Study Drug Related Non-Hematologic Toxicities

Toxicity	Ixabepilone
Grade 3	
Grade 3	Decrease 1 dose
Neuropathy ^c	level ^{a, b}
Grade 3	Decrease 1 dose
Neuropathy	Level ^{a, b}
lasting < 7 days	

Grade 3	Discontinue
Neuropathy	Ixabepilone ^d
lasting ≥⊡7 days	
Grade 4	
Grade 4 toxicity	Discontinue
	Ixabepilone ^d

a. Delay until toxicity resolved to baseline or $\leq \Box$ Grade 1.

b. Patients requiring more than two dose reductions will discontinue Ixabepilone except those who appear to be benefiting from treatment in which case treatment can be continued after consultation with and approval by the Sponsor "The Methodist Hospital Research Institute" (TMHRI).

c. Excludes Grade 3 fatigue/asthenia and transient arthralgia/myalgia for which no dose reduction is required.

d. Responding patients who have sufficiently recovered from toxicity during previous cycle may be considered for retreatment after dose reduction only after discussion with and agreement by Sponsor (TMHRI).

Toxicity	Ixabepilone
Grade 3:	
Grade 3 Platelets	Decrease 1 dose
with: significant	Level ^{a,b}
bleeding or	
requiring platelet	

Dose Modification - Hematologic Toxicities

transfusion	
Grade 4	
Grade 4 Platelets	Decrease 1 dose
	Level ^{a,b}
Grade 4	Decrease 1 dose
Neutrophils lasting	Level ^{a,c}
≥⊡7 days	
Febrile Neutropenia	Decrease 1 dose
any grade	Level ^{a,c}

a. Patients requiring more than 2 dose reductions will discontinue Ixabepilone except those who appear to be benefiting from treatment in which case treatment can be continued after consultation with and approval by the Sponsor (TMHRI)

b. Delay until platelet count ≥□100,000/mm³

c. Delay until neutrophil count $\geq 1,500$ /mm ^{43, 44}

7.3.2. Cetuximab Dose Modifications:

Infusion Reactions

Reduce the infusion rate by 50% for NCI CTC Grade 1 or 2 and non-serious NCI

CTC Grade 3–4 infusion reactions.

Immediately and permanently discontinue cetuximab for serious infusion

reactions, requiring medical intervention and/or hospitalization.45

Dermatologic Toxicity: Recommended dose modifications for severe (NCI-CTC Grade 3 or 4) acneform rash are:

Cetuximab Dose Modification Guidelines for Rash

Severe Acneform	cetuximab	Outcome	cetuximab Dose
Rash Modification			
1st occurrence	Delay infusion 1 to 2 weeks	Improvement	Continue at 250 mg/m ²
		No Improvement	Discontinue cetuximab

2nd occurrence	Delay infusion 1 to 2 weeks	Improvement	Reduce dose to 200 mg/m ²
		No Improvement	Discontinue cetuximab
3rd occurrence	Delay infusion 1 to 2 weeks	Improvement	Reduce dose to 150 mg/m ²
		No Improvement	Discontinue cetuximab
4th occurrence	Discontinue cetuximab		

Patients who experience unacceptable cetuximab toxicity or who are determined to have progressive disease as defined by RECIST during any cycle will be discontinued from the ixabepilone plus cetuximab arm. However if the toxicity is related with cetuximab only; then ixabepilone will be given on a regular basis until the neoadjuvant cycles are completed.

Patients who are deemed not appropriate for further chemotherapy will proceed to local therapy (surgical intervention or radiation therapy).

7.4 Discontinuation of Subjects from Treatment:

Subjects MUST discontinue study treatment (investigational or noninvestigational treatment) for any of the following reasons:

• Withdrawal of informed consent (subject's decision to withdraw for any reason).

• Any clinical adverse event (AE), laboratory abnormality, or intercurrent illness which, in the opinion of the investigator, indicates that continued participation in the study is not in the best interest of the subject.

• Pregnancy.

• Termination of the study by the sponsor, by the local IRB or by the supporting/funding organization Bristol-Myers Squibb (BMS)

• Loss of ability to freely provide consent through imprisonment or involuntary incarceration for treatment of either a psychiatric or physical (e.g., infectious disease) illness.

All subjects who discontinue study treatment should comply with protocolspecified follow-up procedures. The only exception to this requirement is when a subject withdraws consent for all study procedures or loses the ability to consent freely (i.e., is imprisoned or involuntarily incarcerated for the treatment of either a psychiatric or physical illness).

If a subject was withdrawn before completing the study, the reason for withdrawal must be entered on the appropriate case report form (CRF) page.

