2.3.2 Cycle 2 Pre-Infusion Laboratory Visit

• Within 72 hours before beginning the Cycle 2 infusion, obtain blood sample for analysis of albumin, alkaline phosphatase, ALT, AST, total bilirubin, blood urea nitrogen, calcium, chloride, creatinine, glucose, lactic dehydrogenase, potassium, phosphorus, and sodium, as well as complete blood count (Hemoglobin, Hematocrit, RBC, WBC, Platelets) with differential (Neutrophils, Lymphocytes, Monocytes, Eosinophils, Basophils). CrCL "CrCl = [(140 - age) x IBW] / (Scr x 72) (x 0.85 for females)" before every cycle for patients with an abnormal creatinine.

• Laboratory tests comprise of calcium, magnesium, and potassium before every dose of cetuximab therapy (before every cycle for the ixabepilone plus cetuximab arm).

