6.0 Study Population

-Patients with either T1N1-N3M0 or T2-4 N0-3M0 disease who are triple negative and who are candidates for preoperative chemotherapy.

Patients will receive a physical assessment, imaging, a blood draw, and a biopsy prior to the start of treatment.

6.1 Inclusion Criteria:

-Patients with histologic confirmation of invasive breast carcinoma.

-Patients must have intact primary tumor.

-Age \geq 18 years.

-Invasive breast carcinoma must be determined to be ER (-), PR (-) and

HER2Neu (-) prior to study entry.

-Patients should have T1N1-3M0 or T2-4 N0-3M0.

-Patients with bilateral breast cancer are eligible.

-Patients should have a Karnofsky performance scale of \geq 70%.

-Patients must have clinically measurable disease by physical exam to be treated in the neoadjuvant setting.

-Patients should have adequate bone marrow function, as defined by peripheral granulocyte count of \geq 1500/mm³, and platelet count \geq 100000mm³.

-Patients must have adequate liver function with a bilirubin within normal laboratory values. Alkaline phosphatase and transaminases (ALT and AST) may be up to 1.5 x upper limit of normal (ULN) of the institution.

-Patients should have adequate renal function with creatinine levels within normal range.

-Patients should have a normal left ventricular ejection fraction (LVEF) of ≥50%.

-Negative serum or urine pregnancy test for a woman of childbearing potential (WOCBP).

-WOCBP must use a reliable and appropriate contraceptive method during the study and six months after chemotherapy is completed. WOCBP are women who are not menopausal for 12 months or had no previous surgical sterilization. -Patients must sign an informed consent indicating that they are aware of the investigational nature of the study, in keeping with institutional policy.

6.2 Exclusion Criteria:

-Patients with a history of other invasive malignancies diagnosed and treated within the previous 5 years, except non-melanoma skin cancer and non-invasive cervical cancer.

-Her2Neu, ER and PR positive patients should be excluded.

-Patients with an organ allograft or other history of immune compromise.

-Prior treatment with any investigational drug within the preceding 4 weeks.

-Chronic treatment with systemic steroids or another immunosuppressive agent.

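### After a Grade 2 bilirubin rise, section 7.3.1 lets ixabepilone resume at 40 mg/m² while bilirubin is still above the section 6.1 entry limit

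*Combined protocol and SAP*

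**What the plan says.** All references are to the combined protocol and SAP.

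- **Entry (6.1):** "Patients must have adequate liver function with a bilirubin within normal laboratory values". ALT, AST and alkaline phosphatase may be up to 1.5 x ULN.
- **Monitoring (2.3.2, repeated in 2.3.3 and 2.3.4 for cycles 3 and 4):** "Within 72 hours before beginning the Cycle 2 infusion, obtain blood sample for analysis of albumin, alkaline phosphatase, ALT, AST, total bilirubin". No action limit is attached to the result.
- **Dose rules (7.3.1):** The general text says "If toxicities are present, treatment should be delayed to allow recovery". The table headed "Dose Modification - Study Drug Related Non-Hematologic Toxicities" works by grade, with separate rows for neuropathy. Its Grade 2 row, which excludes neuropathy lasting 7 days or more, makes no dose change. Footnote a to that row reads "Delay until toxicity resolved to baseline or" Grade 1 or lower. There is no bilirubin or transaminase row.
- **Discretion (7.4):** Treatment must stop for a laboratory abnormality if the investigator judges that continuing is not in the patient's interest. No numeric limit is given.
- **Pharmacology (10.1, hepatic impairment):** AUC was 22% higher in a group with either bilirubin >1 to 1.5 x ULN, or AST above ULN and bilirubin below 1.5 x ULN. A lower dose is advised for monotherapy in hepatic impairment. Liver testing before and during treatment is advised because the dose needs adjusting to liver function.

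**The concern.** The plan sets a bilirubin limit for entry, measures bilirubin before every later cycle, and explains in 10.1 why liver function should guide the dose. The dosing rules do not join these up. A patient whose pre-cycle bilirubin would have kept her out of the trial may receive the full dose again, although the result is in hand before the infusion.

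What is at stake is the safety of individual patients, through higher ixabepilone exposure than the 40 mg/m² dose is meant to give.

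**Working it through.** The plan states no figure on this point, so there is none to reproduce. The check is a trace through the rules followed by short arithmetic.

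**1. Trace of a bilirubin rise through 7.3.1**

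- *Grade 4, drug-related:* discontinue; footnote d allows retreatment with sponsor agreement.
- *Grade 3, drug-related:* the first Grade 3 row is printed as neuropathy, but its footnote c says "Excludes Grade 3 fatigue/asthenia and transient arthralgia/myalgia for which no dose reduction is required", which suggests that Grade 3 toxicity in general was meant. On that reading the dose falls one level, to 32 mg/m². Read as printed, Grade 3 liver toxicity has no row.
- *Grade 2, drug-related:* delay, then the same dose. The footnote offers two end points joined by an or, so return to the normal baseline is not required. Assumption: Grade 1 bilirubin is above normal (cut-offs are not printed). Then 40 mg/m² may resume above the 6.1 limit.
- *Grade 1:* no table row applies. The general delay sentence has no grade floor and does bear on this case, but it names no threshold and no dose.
- *Judged unrelated to study drug:* outside the table by its title, and so left to general judgement and 7.4.

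**2. Comparison with the hematologic rules**

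| Measure | Entry (6.1) | Re-dosing (7.3.1) |
|---|---|---|
| Platelets | ≥100,000/mm³ | ≥100,000/mm³ |
| Neutrophils/granulocytes | ≥1,500/mm³ | ≥1,500/mm³ |
| Bilirubin | normal | none; baseline or Grade 1 or lower under the general footnote |

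For blood counts, the plan carries the entry limit into re-dosing. For bilirubin it does not.

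**3. Size per affected patient**

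Inputs: dose 40 mg/m² and level -1 of 32 mg/m² (7.3.1); AUC increase 22% (10.1, a point estimate without an interval). Assumptions: AUC is proportional to dose, and the pooled 22% applies to patients with bilirubin >1 to 1.5 x ULN.

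Equivalent dose in normal liver function = dose x (1 + AUC increase).

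- 40 x 1.22 = 48.8 mg/m², or 48.8/40 = 122% of intended.
- 32 x 1.22 = 39.04 mg/m², or 39.04/40 = 97.6% of intended.
- Dose that matches intended exposure: 40/1.22 = 32.8 mg/m², close to level -1.
- Largest AUC increase that level -1 can offset: 40/32 = 1.25, that is 25%.

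For scale, 4.0.2 (CA163-009 and CA163-010) says the dose was cut to 40 mg/m² because 50 mg/m² over 3 hours gave excessive myelosuppression and mucositis in another study. The same section also reports 50 mg/m² as the maximum tolerated dose on a 1-hour schedule in CA163-001, with severe toxicity requiring reduction in 1 of 10 further patients. The comparison is therefore context and does not show harm at 48.8.

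**The case against.** The strongest reply is that the plan is not silent. The graded rows cover any drug-related toxicity, including a laboratory finding; the dose may be lowered for poor tolerance; toxicity calls for delay; 7.4 can require stopping; and 10.1 is itself protocol text advising reduction. On this view the advice exists for Arm 1 and merely sits in another section. Much of this stands: full dose is permitted, not required. But none of these provisions names a liver threshold or a dose, and the one row that fits a Grade 2 rise points to an unchanged dose, against the advice in 10.1.

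A second reply concerns the 22%. The group mixes raised bilirubin with raised AST, and 6.1 already admits AST up to 1.5 x ULN at full dose. Section 10.1 gives no dose by band and does not single out this mildest band for reduction. This stands as a limit on the size: 48.8 mg/m² is an illustration under a stated assumption.

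Third, numbers are likely to be limited: entry requires normal bilirubin, 6.2 excludes chronic liver disease, and there are only four cycles. The documents give no bilirubin event rate, so this can be neither confirmed nor dismissed.

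Stronger readings may tempt a reader, but the documents do not support them:

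- *Re-dosing at bilirubin >1.5 to 3 x ULN, where 10.1 gives a 30% rise (40 x 1.30 = 52.0 mg/m²).* Drug-related toxicity of Grade 2 must first fall to baseline or Grade 1. With no cut-offs printed, it is not shown that the Grade 2 route, or a Grade 1 rise, reaches this band.
- *A cetuximab-only route in Arm 2.* Section 7.3.2 says that if toxicity is due to cetuximab alone "then ixabepilone will be given on a regular basis until the neoadjuvant cycles are completed". This more naturally means keeping the schedule than waiving 7.3.1, and 10.2 lists no liver toxicity for cetuximab.
- *A ban on dosing above normal bilirubin.* The ban in 10.1 is for the capecitabine combination, which neither arm receives.

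**Conclusion.** The point holds in a limited form. The Grade 2 rule in 7.3.1 allows 40 mg/m² to resume with bilirubin above the 6.1 limit, and no other rule supplies a bilirubin threshold or dose. This sits badly with the dosing advice in 10.1 and with the plan's own handling of blood counts.

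The size is about 22% excess exposure per affected patient. It rests on three assumptions: Grade 1 bilirubin is above normal, AUC is proportional to dose, and the pooled estimate carries over to raised bilirubin. The number affected is unknown. A reader should not infer a bias in the pCR comparison; nothing in the documents supports one. The change is an optional, cheap improvement.

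**What to change.** Add a separate line to 7.3.1, outside the table limited to study-drug-related toxicity, and state that it overrides the unchanged dose in the Grade 2 row:

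*Pre-cycle bilirubin >1 to 1.5 x ULN: give no more than dose level -1 (32 mg/m²). Bilirubin >1.5 x ULN: hold until ≤1.5 x ULN, then apply the preceding rule. Any stricter existing rule still applies.*

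The hold is the cautious choice because level -1 offsets an AUC rise of at most 25%, less than the 30% reported for the higher band. No AST or ALT trigger is proposed: 6.1 accepts AST up to 1.5 x ULN at full dose, and 10.1 gives no such cut-off for a lower monotherapy dose. The advice in 10.1 supports the line directly for Arm 1. Applying it to ixabepilone in Arm 2, and choosing 32 mg/m², are judgements made here.

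Cost: one line by amendment. There are no new tests, and entry criteria, starting dose, sample size and analysis are unchanged. The drawback follows from "No dose re-escalation will be allowed after dose reduction": even a transient rise keeps the patient at 32 mg/m² or lower. Of the planned 4 x 40 = 160 mg/m², she then receives at most:

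- from cycle 2: 40 + 3 x 32 = 136 (85%)
- from cycle 3: 80 + 2 x 32 = 144 (90%)
- from cycle 4: 120 + 32 = 152 (95%)

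It also uses one of the two reductions allowed before discontinuation, and a hold can delay a cycle, as footnote a already can.

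### In the ixabepilone non-hematologic dose table (7.3.1), the first Grade 3 row appears mislabelled as neuropathy: it clashes with the stop row at 7 days or more and leaves other Grade 3 toxicity without an assigned action

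*Combined protocol and SAP*

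**What the plan says.** Section 7.3.1 opens with general text. It permits a reduction ("The dose of Ixabepilone may be decreased depending on how well the patient tolerates the study treatment"), calls for a pause ("If toxicities are present, treatment should be delayed to allow recovery") and deals with recurrence ("If toxicities recur, an additional 20% dose reduction should be made"). The dose levels are 40, 32 and 25 mg/m², with no re-escalation.

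The non-hematologic table then has three Grade 3 rows, all labelled neuropathy:

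- Row 1: Grade 3 neuropathy, footnote c, no duration given. Decrease one level (footnotes a and b).
- Row 2: Grade 3 neuropathy "lasting < 7 days". Decrease one level (footnotes a and b).
- Row 3: Grade 3 neuropathy of 7 days or more. Discontinue (footnote d).

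Footnote a requires recovery to baseline or Grade 1 before the next dose. Footnote b limits the number of reductions. Footnote c reads "Excludes Grade 3 fatigue/asthenia and transient arthralgia/myalgia for which no dose reduction is required". Footnote d leaves a narrow way back after stopping: "Responding patients who have sufficiently recovered from toxicity during previous cycle may be considered for retreatment after dose reduction only after discussion with" the sponsor, and with its agreement.

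The Grade 2 block has a general row (no change, except for neuropathy of 7 days or more). The Grade 4 block has a single row for any Grade 4 toxicity.

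**The concern.** Taken literally, the Grade 3 block has two faults. Every patient in row 3 also fits row 1, and the protocol does not say which row prevails. One physician could hold the drug and resume at 32 mg/m² under row 1, while another would stop under row 3, with a restart open only to responders by sponsor agreement. For a patient who is not responding, that is the difference between resuming and stopping. Second, a first Grade 3 non-neuropathy event outside the footnote c exemptions has no assigned action in the table. At stake is the consistency of a safety rule for a cytotoxic drug given in both arms.

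**Working it through.** No sample-size or power figure enters this point. The check is to place each type of Grade 3 non-hematologic event against the rows, first as printed and then with row 1 read as toxicity other than neuropathy.

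| Grade 3 event | Rows met as printed | Action as printed | Action if row 1 means non-neuropathy |
|---|---|---|---|
| Neuropathy under 7 days | 1 and 2 | Decrease one level (row 1 redundant) | Decrease one level (row 2) |
| Neuropathy 7 days or more | 1 and 3 | Decrease one level, or discontinue | Discontinue (row 3) |
| Diarrhea, stomatitis and similar | None | General text only | Decrease one level (row 1) |
| Fatigue/asthenia, transient arthralgia/myalgia | None, but named in footnote c | No reduction | No reduction (footnote c to row 1) |

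One change of label removes both the overlap and the gap. Two features of the table point to it independently:

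1. Footnote c exempts events that are not neuropathies. It has no function on a neuropathy row and fits a row for other toxicity.
2. Grades 2 and 4 each have a general row. Only Grade 3 lacks one.

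Footnote c alone would not be proof. It is also attached to the Grade 2 neuropathy row, where a Grade 3 exemption cannot apply, so the markers are placed loosely. The comparison with Grades 2 and 4 does not depend on it.

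**Dose at stake in the gap.** One level is 40 to 32 mg/m²: (40 − 32)/40 = 20%.

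**Number of patients.** The background figures in 4.0.2 do not yield a usable count.

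- In the neoadjuvant study CA163-080, neuropathy was a serious adverse event in 2 of 161 subjects (2/161 = 1.2%). This counts seriousness, not grade or duration.
- The same study reports Grade 3/4 related events in 25% and Grade 3/4 neutropenia in 14%. The difference, 25 − 14 = 11 percentage points, still contains other blood counts, Grade 4 events, neuropathy and exempt events. It omits neutropenic patients who also had another event.
- In CA163-081, Grade 3-4 sensory neuropathy took a median of 5.4 weeks to resolve (5.4 × 7 = 38 days). Episodes beyond 7 days are therefore realistic, although those patients were heavily pretreated.
- Only events followed by another cycle matter, and section 2.1 allows at most four cycles. The documents do not give the share of events with a cycle still to come.

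**The case against.** The strongest reply is that the intent is clear. Rows 2 and 3 already divide all Grade 3 neuropathy at 7 days, so reading row 1 as neuropathy makes row 2 redundant and footnote c pointless. A careful reader would let the specific row govern. That largely answers the overlap. It leaves the gap, which the reader must fill by inference.

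A second reply is that a word may have been lost when the table was read from PDF; the Grade 2 row has an *except* at the matching place. This cannot be excluded. Against it, the neuropathy label and marker c stand in the same cell, and the Grade 2 wording survived. The source page should be checked first.

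Third, there are safeguards. Under row 1 the patient must first recover to baseline or Grade 1 and returns at a lower dose. Footnote d restricts restart after stopping. Section 7.4 requires discontinuation when the investigator judges that continuing is against the patient's interest. This is also one institution, which is itself the sponsor, so differences in practice should be small. All of this stands and lowers the severity.

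Two stronger readings are tempting but unsupported:

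- A reader might infer that 40 and 32 mg/m² are equally acceptable after a first Grade 3 diarrhea. The permissive opening sentence allows that reading. But footnote c names the events that need no reduction, which implies that others do, and the *additional* reduction on recurrence presupposes an earlier one.
- A reader might take the neuropathy background in 4.0.2 as support for row 1. It says that earlier studies discontinued the drug until recovery and then reduced the dose. That fits row 3 with footnote d just as well, so it does not favor either row.

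**Conclusion.** The concern holds as a minor dosing-table correction. As printed, Grade 3 neuropathy of 7 days or more meets two rows with different actions, and no row assigns an action to other Grade 3 non-hematologic toxicity. Row 1 was almost certainly meant for toxicity other than neuropathy. This rests on the table as extracted being faithful to the source page.

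Few patients are likely to be affected, and the number cannot be estimated reliably from the documents. A reader might infer a threat to the trial's result, but nothing here supports that. The rule applies to ixabepilone in both arms, and the sample size, the pCR definition and the intention-to-treat analysis do not depend on it.

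**What to change.** Check the source table first. If it matches the text as read, then in the next amendment:

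- Relabel row 1 *Grade 3 toxicity other than neuropathy*, keeping footnote c and the one-level decrease after delay.
- Keep the under-7-days row and the 7-days-or-more row as the only Grade 3 neuropathy rules.
- Leave two existing rules in force alongside the new label: no retreatment after a severe hypersensitivity reaction (7.1 and 7.2), and the cetuximab-only rule in 7.3.2 ("However if the toxicity is related with cetuximab only; then ixabepilone will be given on a regular basis until the neoadjuvant cycles are completed").
- Optionally, remove footnote c from the Grade 2 neuropathy row.

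The cost is a wording change to one table, with no extra patients, visits or procedures.
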